### **Primary Objective**

The primary objective of this multi-faceted implementation trial is to determine the impact, if any, of use of teaching, technology or facilitated referral to a dedicated third party team (virtual GDMT) contracted by Biofourmis on:

**TRANSFORM:** GDMT baseline enrollment to 9 month change in prescription of the main classes of drugs (receiving 50% or higher of target doses for HF patients) for the relevant disease states among eligible patients

### **Subanalysis for each disease state:**

T2D/ASCVD:

- a. the proportion of treatment-naïve patients who are newly prescribed a SGLT2i and/or GLP-1RA over 9-months
- b. Rate of medication persistence: % of patients on a SGLT2i and/or GLP-1RA at baseline who remained on a SGLT2i and/or GLP-1RA during the study period

HFrEF: For those with HFrEF, baseline to 9 months change in average composite endpoint of at least 50% target dose achievement for the main classes of drugs (RASi/beta blockers/MRA/SGLT2i) among eligible patients.

- a. Goal doses will be based on the 2020 ACC Expert Consensus Decision Pathway for Optimization of Heart Failure Treatment (4).
- b. To calculate this composite:
  - i. Numerator = receiving ARNI/ACEI/ARB at 50% or higher of target dose + receiving evidence-based beta blocker at 50% or higher of target dose + receiving MRA at 50% or higher of target dose + receiving SGLT2i at 50% or higher of target dose.
  - ii. Denominator = eligible to receive ARNI/ACEI/ARB, eligible to receive evidence-based beta blocker, and eligible to receive MRA, and eligible to receive SGLT2i.
  - iii. Using this approach, each patient may contribute to the numerator or be in the denominator 1, 2, 3 or 4 times, depending on meeting criteria and if eligible in that domain. An advantage of this composite approach is that it allows for a holistic view of all classes of drugs considered and allows for assessment not only of up-titration but also down-titration as well.
- c. Rate of medication persistence: % of patients on medications at baseline who remained on medications during the study period

Page Break

#### HFpEF:

For those with HFpEF, baseline to 9 months change in average composite endpoint of target dose achievement for the main classes of drugs (RASi/MRA/SGLT2i) among eligible patients.

- a. Goal doses will be based on the 2020 ACC Expert Consensus Decision Pathway for Optimization of Heart Failure Treatment (4) and 2022 Heart Failure Guidelines.
- b. Calculation similar to the above for HFpEF using the three relevant classes
- c. Rate of medication persistence: % of patients on medications at baseline who remained on medications during the study period

AF: Total proportion of eligible patients with an OAC prescription at baseline and 9 months

- a. Rate of OAC initiation: % of patients not on OAC at baseline who were started on OAC during the study period
- b. Rate of OAC persistence: % of patients on OAC at baseline or who started OAC thereafter who remained on OAC during the study period

All outcomes data will be stratified by the following subgroups: age, race, sex, socioeconomic status, English vs non-English speaking.

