**Population:**

**750 total with comorbidity overlap (250 HFrEF, 250 HFpEF, 500 AF, 250 T2D/ASVD)**

*Inclusion criteria:*

1. Age  $\geq 18$  years
2. Personal access to a computer and/or smartphone for app download
3. Heart Failure (reduced and preserved ejection fraction) AND/OR
4. Atrial Fibrillation with CHA2DS2-VASc score greater than or equal to 2 in men and greater than or equal to 3 in women AND/OR
5. T2D and ASCVD, defined as follows:
  - a. Known CAD, prior ACS, or coronary artery revascularization
  - b. Prior TIA/stroke or known carotid or intracerebral atherosclerosis
  - c. Prior PAD including requiring revascularization

*Exclusion criteria:*

- All patients
  - Current or anticipated participation in an interventional clinical trial of a drug/device
  - Currently receiving comfort care or enrolled in hospice
  - Life expectancy <1 year
  - Pregnancy or active breastfeeding
  - Current or anticipated participation in an interventional clinical trial (other than TRANSFORM GDMT)
  - Patients without a clinical encounter within three years of study start date
- Heart Failure patients:
  - History of or plan for heart transplantation or left ventricular assist device
  - Palliative chronic inotropic therapy
  - NYHA Class 4 heart failure
- Atrial Fibrillation patients:
  - Current prescription for OAC
  - Reversible cause of atrial fibrillation, such as post-cardiothoracic surgery or thyrotoxicosis
  - History of ischemic stroke in prior 7 days
  - Transient ischemic attack in prior 3 days
  - Platelet count <70,000/ml
  - Hemoglobin concentration <8g/dl
  - History of or condition associated with increased bleeding risk, such as hemophilia
  - History of mechanical valve replacement
  - Major surgical procedure or trauma within 14 days
  - Clinically significant gastrointestinal bleeding within 8 weeks

- History of intracranial, intraocular, spinal, or atraumatic intra-articular bleeding
- T2D/ASCVD patients with or without HF or AF:
  - Current prescription for SGLT2i and GLP-1RA
  - Current or planned hemodialysis
  - Decompensated end stage liver disease
  - Type 1 diabetes
  - Prior diabetic ketoacidosis
  - Gestational diabetes
  - History of pancreatitis or pancreatic cancer

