## **Research Question, Objectives & Aims**

---

The goal of this implementation trial is to evaluate several clinician and patient-facing implementation strategies to increase adherence to guideline recommended care and to increase prescription of evidence-based therapies proven to reduce the risk of cardiovascular outcomes in patients, HF, AF and T2D/ASCVD.

Patients will be randomized to 1 of 3 implementation strategies conducted over 9 months: 1) clinician and patient education; 2) technology + clinician and patient education +; 3) referral to

third party virtual team (GDMT team) contracted by Biofourmis+ clinician and patient education. Patients will be followed for 9-months to evaluate for changes in the % of patients who ever receive new CV risk reduction therapies by type of strategy. We hypothesize that care of patients with HF, AF, and T2D/ASCVD, including underserved populations and those with health care disparities historically, can be effectively and safely optimized with support outside traditional ambulatory care encounters.

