- B) **Technology + Education:** This implementation strategy will leverage technology to apply “audit and feedback” of prior care to inform recommendations for future care. These suggestions will encompass the domains of GDMT medications based on eligibility and potential opportunity for an SGLT2i, GLP-1RA, ACEi/ARB, antiplatelet or antithrombotic therapy, and statin therapy, beta blocker, RASi, MRA and DOAC or warfarin. The incorporation of technology for opportunities for GDMT will be utilized to identify tailored opportunities for each CV medication based on guideline recommendations. Clinicians will be presented individual patient-specific recommendation(s) for further optimization of GDMT approximately every two weeks.

Specifically, an EHR data extractor or data entry form will process data to Biofourmis, where a dashboard will be created. This dashboard will include a) lists of eligible patients for the study and b) an update on opportunities for further medication optimization. The latter information will be based on guideline-directed medical targets as articulated in the ACC clinical policy. Guidance regarding post-initiation monitoring strategies will be additionally included. A patient facing tool will be connected to the dashboard for patient education, surveying, medication adherence, patient reported outcomes, and patient recorded data.

- C) **Referral Support + Education:** Each site will have referral access to a virtual GDMT team (TRANSFORM). Primary care physicians or cardiologists caring for patients randomized to this intervention strategy will receive notification of the referral. All patients randomized to this group will be considered in this group whether or not the referral to the virtual GDMT team is completed. Care in this group will be supported by the same technology as arm B with the same standardized opportunities for improvement. The virtual GDMT team will have access to data entered into the Biofourmis platform from the EHR and/or supplemented by standard patient interviews. The virtual team will follow an every two week medication review schedule for possible adjustments until GDMT optimization has been completed.

In order to standardize education about best practices surrounding GDMT directed care (to establish a cognitive baseline), educational materials will include a “suite of tools” shared with all clinicians.

Quality Improvement strategies and resources for all arms will include:

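### The AF persistence rate counts patients who start OAC after randomisation and stops the clock at month 9, so it cannot be compared between arms

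*Protocol*

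**What the plan says.** The AF part of the Protocol's subanalysis by disease state leads with the proportion of eligible patients prescribed OAC at baseline and at 9 months. Two sub-items follow:

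- Item (a), initiation: the percentage "of patients not on OAC at baseline who were started on OAC during the study period".
- Item (b), persistence: the percentage "of patients on OAC at baseline or who started OAC thereafter who remained on OAC during the study period".

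Follow-up is fixed: "Patients will be followed for 9-months to evaluate for changes in the % of patients who ever receive new CV risk reduction therapies" (Research Question, Objectives & Aims). Item (b) sets no window counted from the date of starting.

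Three other statements bear on this:

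- The AF exclusion criteria (Study Design, Population) list "Current prescription for OAC".
- Research Methods describes arm B as follows: "Clinicians will be presented individual patient-specific recommendation(s) for further optimization of GDMT approximately every two weeks". For arm C: "The virtual team will follow an every two week medication review schedule for possible adjustments until GDMT optimization has been completed". No such cycle is described for arm A, education alone.
- The other persistence rates use baseline users only. For T2D/ASCVD it is the percentage "of patients on a SGLT2i and/or GLP-1RA at baseline who remained on a SGLT2i and/or GLP-1RA during the study period", and for HFrEF the percentage "of patients on medications at baseline who remained on medications during the study period". HFpEF is worded like HFrEF.

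**The concern.** Item (b) has two separate problems.

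**Selection.** A patient not on OAC at entry joins the denominator only by starting it, which is the event counted in item (a) and the event the strategies are meant to bring about. The groups compared across arms are therefore formed by response to the assigned strategy, and randomisation no longer protects the comparison.

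**Unequal time at risk.** A patient who starts in month 8 has about one month in which to stop, and one who starts in month 1 has eight. Whether remaining on OAC means continuous use or use at month 9, exposure ends at month 9. The two-weekly cycles in arms B and C give good reason to expect earlier starts there than in arm A.

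The T2D/ASCVD, HFrEF and HFpEF rates avoid both problems, because all their patients are on drug at baseline and share one 9-month window. At stake is a reading, by arm, that anticoagulation started through the more active strategies does not last, when the stopping rate is the same.

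**Working it through.** The Protocol states no persistence rate, stopping rate or start time for OAC, so there is no figure to reproduce. Stopping rates and start times below are assumptions. The 9-month end, the denominator and the exclusion come from the Protocol.

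**1. Starters only (exclusion enforced), same stopping in both arms.** With monthly stopping risk m, a patient starting at month s is still on OAC at month 9 with probability (1 − m)^(9 − s). For m = 3%: start at month 1 gives 0.97^8 = 78.4%; month 3 gives 0.97^6 = 83.3%; month 5 gives 0.97^4 = 88.5%.

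| m per month | Start month 1 | Start month 3 | Start month 5 | Gap, 1 vs 3 | Gap, 1 vs 5 |
|---|---|---|---|---|---|
| 1% | 92.3% | 94.1% | 96.1% | 1.9 | 3.8 |
| 2% | 85.1% | 88.6% | 92.2% | 3.5 | 7.2 |
| 3% | 78.4% | 83.3% | 88.5% | 4.9 | 10.2 |
| 5% | 66.3% | 73.5% | 81.5% | 7.2 | 15.1 |

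Gaps are in percentage points, from unrounded values. The earlier start always has the lower rate.

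**2. Starts spread over time.** Use a constant rate h = 0.03 per month and average exp(−h(9 − s)) over the start times.

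- Months 0 to 9: (1 − e^−0.27)/0.27 = 87.6%.
- Months 0 to 6: (e^−0.09 − e^−0.27)/0.18 = 83.6%. The gap is 4.0 points.
- All at month 1: e^−0.24 = 78.7%. The gap from months 0 to 9 is about 9 points.

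**3. Front-loaded stopping.** Take a Weibull curve with shape 0.5 and 25% stopped by 9 months. Eight months at risk gives 76.2% and four months gives 82.5%, a gap of 6.3 points.

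**4. Baseline users mixed in.** They have the longest exposure, 9 months.

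- Equal shares in both arms, m = 3%, starts at month 1 vs month 5. With 20% baseline users the rates are 77.9% vs 86.0%. With 50% they are 77.2% vs 82.3%. The gap falls from 10.2 to 8.1 and 5.1 points.
- Equal numbers, but unequal numbers of starters. Let each arm hold 30 baseline users, with h = 0.03, so that each remains on OAC with probability e^−0.27 = 0.763. Arm A has 10 starters over months 0 to 9: (30 × 0.763 + 10 × 0.876)/40 = 79.2%. Arm C has 40 starters over months 0 to 6: (30 × 0.763 + 40 × 0.836)/70 = 80.5%. The earlier-starting arm now looks slightly better. If all 40 start at month 1, arm C has (30 × 0.763 + 40 × 0.787)/70 = 77.7%, a deficit of 1.5 points.

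**5. After the change.** With a 3-month window from each patient's own start, among those starting by month 6, every arm has (1 − m)^3: 97.0%, 94.1%, 91.3% and 85.7% for m = 1%, 2%, 3% and 5%. The artefact from unequal exposure is 0.

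**The case against.** The best case for the plan runs as follows. The measure that does support a randomised comparison, OAC prescription at 9 months, already leads the AF list, and item (b) sits beneath it. The Protocol states no test or contrast for item (b), and an analysis plan that is not shown could add a window, a time-to-event method or a descriptive label. Start times are guesses: in arm C they depend on referral completion and on clinician choice, which is unrestricted. AF is not powered.

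Much of this stands, and it limits the point. It does not remove it. The Protocol itself fixes the denominator and the period, and those two create the bias, so this is not missing detail. The subanalysis sits under a primary objective about the impact of the strategies, so the rate will naturally be read by arm.

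A reader might infer that the faster arm must always look worse. The documents do not support that. The definition counts baseline users while the AF exclusions bar them, and step 4 shows that their presence can cancel or reverse the gap. A reader might also take a gap of 9 or 10 points as the expected size. That rests on nearly all early starts falling at month 1, which nothing in the Protocol establishes.

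**Conclusion.** The concern holds in a limited form. As written, item (b) conditions on a post-randomisation event and gives patients unequal time at risk, so it is not a valid comparison between arms, whatever the direction of the bias. The direction is determined only if current OAC users are in fact excluded, so that starters dominate; the earlier-starting arm then looks less persistent under identical stopping.

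On the assumed rates of 1% to 5% per month and the single start months in step 1, the false gap is roughly 2 to 15 points. At 3% per month it is about 4 to 10 points across the start patterns tried with a constant stopping rate. The documents cannot narrow this further.

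A reader might infer that the trial's main result is threatened. It is not: this is a sub-item in a disease state for which the Protocol does not expect adequate power, and the primary comparison does not use it.

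**What to change.** 1. Reconcile the AF exclusion of current OAC users with the part of item (b) that counts patients on OAC at baseline, and state whether such patients can enter the AF analysis.
2. State that the randomised AF comparison is the proportion of all eligible randomised AF patients on OAC at 9 months. It reflects both starting and stopping.
3. Report persistence separately for baseline users, if any, and for starters.
4. For starters, use a fixed window from each patient's own start (for example 90 days, among those starting at least 90 days before month 9) or time to discontinuation. Label it descriptive and not a randomised comparison: either method deals with unequal exposure, but neither removes the selection.

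The cost is wording and modest programming. Late starters drop out of the fixed-window rate. The section on mixed methods evaluation already plans to collect the timing of prescriptions, but this rate also needs OAC status at the window's end, or stop dates, extracted from the EHR.

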#### **Secondary Objective**

##### TRANSFORM:

1. Difference in patient reported outcome scores specifically;
  - a) Difference in patient reported outcomes on Morisky Medication Adherence Scale (MMAS-4) from baseline, 3 and at 9 months
  - b) Difference in patient reported outcomes on Patient Activation Measure® (PAM) from baseline, 3 and at 9 months
  - c) Difference in patient-reported outcome/KCCQ-12 scores from baseline to 9 months (applicable to HFrEF and HFpEF study cohorts only)

#### **By Disease State:**

##### T2D/ASCVD:

1. greater use of guideline-directed cardioprotective therapies
2. improved metabolic parameters (body weight, BMI, HbA1c, systolic BP, lipid levels)
3. lower total daily insulin dose (among patients on any insulin at baseline)
4. Proportion of eligible patients with visits with an opportunity to discuss GDMT during the study period

##### HFrEF:

1. Relative change in actual achieved doses of individual classes of pivotal therapies (RASi/beta blocker/ MRA/SGLT2i).
2. Relative change in achievement of target doses (yes/no) of pivotal therapies (RASi/beta blocker/MRA/SGLT2i).

3. Proportion of eligible patients with visits with an opportunity to discuss GDMT during the study period

#### HFpEF

1. Relative change in actual achieved doses of individual classes of pivotal therapies (RASi/MRA/SGLT2i).
2. Relative change in achievement of target doses (yes/no) of pivotal therapies (RASi/MRA/SGLT2i).
3. Proportion of eligible patients with visits with an opportunity to discuss GDMT during the study period

#### AF:

1. Proportion of eligible patients with visits with an opportunity to discuss OAC during the study period

#### **Implementation Efficacy Measures:**

- We will assess engagement with the technology and referral completion rates by patients
- Short questionnaires (PAM, MMAS-4, KCCQ-12, CardioSmart E-Diary) will be completed at baseline by patient participants to determine any patient factors that may modify the responses to each of the intervention arms (centered around baseline perception of care optimization, perceived cardiovascular risk, willingness to take new therapy, clinician trust / therapeutic relationship). See appendix.

#### **Research Methods**

---

All eligible patients (see detailed inclusion/exclusion criteria above) with HF, AF and/or with T2D/ASCVD, who are not currently treated on optimal GDMT will be identified across all health systems.

All eligible patients will be randomized to 1 of the 3 implementation approaches and remain under the randomized strategy for the remainder of the study (following intention-to-treat principles). Even if the patient changes PCP or cardiologist (expected low frequency), patients will continue to receive the care under the arm in which they were randomized to. The interventions will be clinician-facing and we chose to select PCP and cardiologists as the target for quality improvement for several reasons: 1) PCPs represent a large cohort of clinicians across health systems, serving as the entry of care and access point for specialty referrals; 2) Patients are unlikely to change PCPs and cardiologist during the short-term duration of the study; 3) Most or all patients are assigned a PCP in a health system thus allowing for clear clinician attribution; 4) PCPs and cardiologists may have sufficient exposure and comfort with prescription of these risk reduction therapies to allow successful intervention to action. If patients leave the health system entirely, then the participant will be censored as lost to follow-up.

**Randomization Scheme:** Patients will be randomized 1:1:1 to the 3 quality improvement strategies using a standardized randomization software within the Biofourmis platform. To ensure adequate power, enrollment will only end when all three arms have met their individual targets for

patient accrual in both disease categories and representation of underserved populations and those with health care disparities historically across sites. Enrollment of patients with comorbidities will be accomplished through prospective patient identification of patients eligible by disease state and focus populations.

- A) **Clinician and Patient Education:** This implementation strategy will support engaging the patients with their existing clinicians using a CardioSmart materials to guide treatment expectations. Clinicians also will receive education on the latest medications for CV risk management. There is no “placebo” arm.
- B) **Technology + Education:** This implementation strategy will leverage technology to apply “audit and feedback” of prior care to inform recommendations for future care. These suggestions will encompass the domains of GDMT medications based on eligibility and potential opportunity for an SGLT2i, GLP-1RA, ACEi/ARB, antiplatelet or antithrombotic therapy, and statin therapy, beta blocker, RASi, MRA and DOAC or warfarin. The incorporation of technology for opportunities for GDMT will be utilized to identify tailored opportunities for each CV medication based on guideline recommendations. Clinicians will be presented individual patient-specific recommendation(s) for further optimization of GDMT approximately every two weeks.

Specifically, an EHR data extractor or data entry form will process data to Biofourmis, where a dashboard will be created. This dashboard will include a) lists of eligible patients for the study and b) an update on opportunities for further medication optimization. The latter information will be based on guideline-directed medical targets as articulated in the ACC clinical policy. Guidance regarding post-initiation monitoring strategies will be additionally included. A patient facing tool will be connected to the dashboard for patient education, surveying, medication adherence, patient reported outcomes, and patient recorded data.

- C) **Referral Support + Education:** Each site will have referral access to a virtual GDMT team (TRANSFORM). Primary care physicians or cardiologists caring for patients randomized to this intervention strategy will receive notification of the referral. All patients randomized to this group will be considered in this group whether or not the referral to the virtual GDMT team is completed. Care in this group will be supported by the same technology as arm B with the same standardized opportunities for improvement. The virtual GDMT team will have access to data entered into the Biofourmis platform from the EHR and/or supplemented by standard patient interviews. The virtual team will follow an every two week medication review schedule for possible adjustments until GDMT optimization has been completed.

In order to standardize education about best practices surrounding GDMT directed care (to establish a cognitive baseline), educational materials will include a “suite of tools” shared with all clinicians.

Quality Improvement strategies and resources for all arms will include:

- Population Identification & Reporting

- Quality Ambassadors
- Communications
- Education

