**The final Statistical Analysis Plan (SAP) will be finalized prior to the study completion.**

**Patient-Level Randomization to 3 Quality Improvement Initiative:** Simple (traditional) randomization minimizes variation in clinical profiles of patients included in each arm. While cluster randomization at the clinician level may limit the potential for contamination bias (chance that clinicians caring for patients randomized to one implementation approach may influence the care of another patient on their panel), the number of eligible patients under each individual clinician's care is anticipated to be small.

**Power Estimates:** In this 3-arm trial, stratified by study site, we estimated the sample size of patients needed to show a difference between the quality improvement arms.

Current estimates of use of either SGLT2i or GLP-1RA among eligible patients is 15%. Assuming an alpha of 0.05, we would require 121 patients in each of the 3 arms to show 80% power to detect at least an absolute difference of 15% between education alone and the education + decision support arms and a 15% between education alone and the education + decision support + facilitated referral group. Assuming a 20-25% loss to follow-up rate, 750 patients would be required.

Current estimates of optimal GDMT prescription and titration for HFrEF are 2%. The differences for each arm are expected to be greater than the SGLT2i or GLP-1RA classes.

Given the evolving evidence for HFpEF, there are no established rates for GDMT.

Current estimates of optimal use of anticoagulation medication for AF is 60-65%. The study does not anticipate reaching power for this disease state.

The primary comparison will be between the education alone arm (1) and the education + decision support + referral group (3). Secondary analyses will compare education alone (1) with the education + decision support group (2). The study will be powered for both primary and secondary comparisons for T2D/ASCVD and HF (HFrEF and HFpEF combined).

Rates of Primary Endpoint Over 9 months			Estimated Number of Patients in Each of 3 Arms			
Education Alone (1)	Education +Decision Support (2)	Education+Decision+Referral Support (3)	80% power		90% power	
			1 vs 2	1 vs 3	1 vs 2	1 vs 3
0.05	0.075	0.1	1471	435	1969	582
0.1	0.15	0.2	686	199	918	266
0.125	0.1875	0.25	529	152	708	203
0.15	0.3	0.3	424	121	568	161

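### The protocol claims 80% power for T2D/ASCVD at 121 per arm, but its 250 planned patients give about 83 per arm, and the closing rule states no targets that would make up the gap

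*Protocol*

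**What the plan says.** Three parts of the protocol bear on this point.

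- **Cohort sizes.** Study Design, Population, gives "750 total with comorbidity overlap (250 HFrEF, 250 HFpEF, 500 AF, 250 T2D/ASVD". The Patient Recruitment table near the front repeats these figures. They are totals over all arms, and a patient may count in more than one cohort.
- **Power.** Statistical Methods, Power Estimates, starts from 15% use of SGLT2i or GLP-1RA and a difference of 15 percentage points: "we would require 121 patients in each of the 3 arms to show 80% power". Loss comes after that figure: "Assuming a 20-25% loss to follow-up rate", the total is put at 750. On scope it says "The study will be powered for both primary and secondary comparisons for T2D/ASCVD and HF (HFrEF and HFpEF combined"). On AF it says "The study does not anticipate reaching power for this disease state".
- **Closing rule.** Research Methods, Randomization Scheme, sets 1:1:1 allocation and then states when recruitment stops: "To ensure adequate power, enrollment will only end when all three arms have met their individual targets for". What those targets cover is described, without figures, as "patient accrual in both disease categories and representation of underserved populations and those with health care disparities historically across sites". No per-arm target by disease category appears there or elsewhere in the protocol.

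**The concern.** The power section makes a claim about T2D/ASCVD as a disease state, not only about the trial as a whole. The planned cohort, divided by three, is smaller than the per-arm number that the same protocol requires, even before any patient is lost. A reader would expect a closing rule justified by power to prevent this, but the rule points to targets that are not written down.

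At stake is how the T2D/ASCVD result is read. A non-significant difference from a comparison described as 80% powered would be taken as fair evidence against a 15-point effect. With close to even odds of detecting that effect, it would not be.

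**Working it through.** **Inputs.** Control rate 0.15, difference 0.15, alpha 0.05, power 80% and loss 20-25% come from Power Estimates. Allocation 1:1:1 comes from Randomization Scheme. The cohort totals come from Population. The protocol does not say whether alpha is one- or two-sided.

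**1. The plan's own figure.** Normal approximation, pooled variance under the null, two-sided 5%:

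n = [1.960 × √(2 × 0.225 × 0.775) + 0.842 × √(0.15 × 0.85 + 0.30 × 0.70)]² / 0.15²

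= [1.960 × 0.5906 + 0.842 × 0.5810]² / 0.0225 = 120.5, so 121 per arm.

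This matches the protocol. A one-sided test would give 95, so two-sided is the reading that fits. In the power table the bold row also shows 424 for arm 1 against arm 2. That figure belongs to 15% against 22.5%, is a separate matter, and is not used here.

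**2. What 250 patients give.** 250 / 3 = 83.3, about 83 per arm. After loss, 83 × 0.80 = 66 and 83 × 0.75 = 62.

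Power = Φ[(0.15 × √n − 1.960 × 0.5906) / 0.5810]

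| T2D/ASCVD patients per arm | Basis | Power, 15% vs 30% |
|---|---|---|
| 121 | stated requirement | 80% |
| 83 | 250 / 3, no loss | 64% |
| 66 | 20% loss | 54% |
| 62 | 25% loss | 52% |

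**3. Detectable difference.** Solving the formula in step 1 for the difference from 15% at 80% power gives 21.1 points at 66 per arm and 21.8 points at 62 per arm.

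**4. What 121 per arm would require.** Without loss, 3 × 121 = 363. With loss, 121 / 0.80 = 151.3, so 152 per arm and 456 in total; 121 / 0.75 = 161.3, so 162 per arm and 486 in total. The plan has 250.

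**5. HF combined.** At most 500 / 3 = 167 per arm, or 133 and 125 after 20% and 25% loss. Power is 84% and 81% if the T2D/ASCVD rates are borrowed. The protocol gives no such rates for HF: it quotes 2% for HFrEF and says none are established for HFpEF.

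**6. The closing rule, read both ways.**

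- *Targets are the Population totals divided by three.* The T2D/ASCVD target is met at about 83 per arm, 38 short of 121 before loss.
- *Targets are 121 per arm in the two categories that the power section names.* T2D/ASCVD then needs at least 363 patients, so the 250 in the recruitment table and in Population is wrong.

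Neither reading makes the three sections agree.

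**The case against.** The strongest reply is that the protocol never divides its cohort totals by three. The closing rule speaks of two disease categories, and the power section names exactly two powered units, T2D/ASCVD and HF combined. On that reading the rule keeps enrolment open until each has 121 per arm, and nothing closes at 83. This reading is at least as good as the other, so 83 cannot be called the target that the rule sets. The conflict remains, because the cohort total of 250 is then too low. Treating 250 as a minimum does not help either, since nothing written secures 121.

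A second reply is that the trial has 750 patients, 250 per arm, or about 187-200 after loss, which is well above 121. That stands for the primary objective, which covers all disease states. It does not stand for a power statement about T2D/ASCVD alone.

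A reader might infer three stronger points that the document does not support:

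- *That the AF goal of 500 contradicts the admission that AF is not powered.* AF may lie outside the closing rule altogether, and a recruitment goal for an openly unpowered disease state is no contradiction.
- *That the lack of a number for underserved representation is an error of the same kind.* It is missing detail and conflicts with no stated figure.
- *That the loose wording on site stratification puts the comparison at risk.* Patients are randomised individually and a site-stratified analysis is planned, so it changes no result here.

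**Conclusion.** The point holds for T2D/ASCVD. The planned 250 patients give 64% power for 15 points with no loss and about 52-54% after the protocol's own loss assumption, against the 80% stated. The design has 80% power only for about 21-22 points. The closing rule cannot be relied on to correct this, because its targets are not given and either plausible reading conflicts with another section.

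The document does not show that the trial as a whole is underpowered, and the all-disease primary composite is not affected by this shortfall. HF combined reaches 81-84% only on borrowed rates.

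The figures assume equal arms, a two-sided 5% test of two proportions, the stated 15% and 30% rates, and all 250 patients contributing. The sub-analysis of new prescriptions counts treatment-naïve patients only. If some of the 250 are already treated, its power is lower still; the protocol gives no count, so no figure is attached.

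**What to change.** - **Statistical Methods, Power Estimates.** Withdraw the statement that the study is powered for T2D/ASCVD, or restate it as what 250 patients deliver: about 52-54% power for 15 points after loss, or 80% power for about 21-22 points.
- **Research Methods, Randomization Scheme.** Name the two disease categories, give per-arm numbers that agree with the recruitment table, Population and Power Estimates, and say whether AF governs closing. This should not be left to the SAP: "The final Statistical Analysis Plan (SAP) will be finalized prior to the study completion", which does not guarantee that it precedes the end of enrolment.

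The cost is wording and a less favourable stated power. Keeping the 80% claim instead would mean 456-486 T2D/ASCVD patients, 61-65% of the 750 (456 / 750 and 486 / 750) in place of 33% (250 / 750), or a larger trial. That is not a cheap change. If enrolment has already ended, report the T2D/ASCVD numbers reached in each arm and the precision they give.
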